## Investigation of Ambulatory Blood Pressure in Cirrhosis Patients AmbBP-C Study

### Hypothesis

We will test the hypothesis that a proportion of patients with cirrhosis experience hypotension in the ambulatory setting, and this occurrence is associated with significant morbidity (e.g., acute kidney injury) and mortality.

### Aims:

What is the burden of masked hypotension (i.e., Proportion of patients with normal clinic visit mean arterial blood pressure but with >1 episode of ambulatory hypotension)?

What is the association between ambulatory blood pressure and clinic visit blood pressure and the development of acute kidney injury?

What is the association between ambulatory blood pressure and clinic visit blood pressure and death?

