### Design:

This is an observational study. We will approach patients with cirrhosis who are seen at the outpatient UCSF Liver Clinics. If willing, patients will be provided an ambulatory blood pressure monitor with an integrated cellular signal (i.e., not wifi or bluetooth) that is listed on the US Blood Pressure Validated Device database (VDL). After an instructional meeting at the time of enrollment, participants will be asked to take their ambulatory blood pressure twice daily (i.e., morning and night). Participants will partake in this study for 1-year. The ambulatory data will be provided to the researchers through an encrypted, HIPAA compliant server provided by the blood pressure monitor manufacturer (i.e. Withings). Simultaneously, we will periodically (i.e., monthly) review the participant's medical records and will extract clinic visit notes including clinic visit blood pressure measurements, demographics, hospitalization records, and all available laboratory values. After 1-year, the cellular signal on the device will be disabled. The participant will be able to keep the device for their own personal use. After 1-year, we will review their records every 6 months for an additional 2-years (3-years total). We will investigate the proportion of patients who experience masked hypotension. We will determine the association between ambulatory blood pressure and clinic visit blood pressure and the development of AKI and mortality.

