### **Procedures/Methods:**

Patients will undergo the following procedures to this study:

1. We will pre-screen patients coming to the UCSF outpatient liver clinic 48 hours prior to their visit.
2. To set the device and allow for distribution at the time of their visit, we will call all possible participants 48 hours prior to their clinic visit and determine if they are interested in partaking in this study.
3. After their clinic visit, potential participants will be approached and provided the consent for this study. If willing, participants will be enrolled, provided a 5-minute device tutorial, and participants will be given the device on their visit day.
4. After which, participants will complete a morning blood pressure (e.g., prior to breakfast) and nighttime blood pressure (e.g., prior to sleep) for 1-year.
5. Patients at the time of enrollment will elect if they would like free text message reminders if they do not complete their measurements for a 24-hour period. If participants, do not complete their measurements for a 72-hour period, then a member of the research team will call them to remind all patients.
6. Should patients be hospitalized or traveling, we will instruct patients to not perform any measurements.
7. All measurements will be provided to the researchers through an encrypted, HIPAA compliant portal provided by the manufacturer (Withings).
8. We will review their medical records monthly for a 1-year period and every 6 months for an additional 2-year period. This review will include all clinic notes, demographics, and laboratory values.

There will be no extra clinic visits, lab tests, biopsies, tissue collection, or additional scans outside the routine care and monitoring provided by the UCSF Liver Clinic. We will not monitor the portal for episodes of hypotension in real-time - meaning that if a patient has hypotension, they will not be called to review for symptoms. Instead, at the time of consent and the monitor tutorial, we will review with patients the signs and symptoms of hypotension. We will instruct patients to review any new developments with their provider, who can be reached 24 hours 7-days a week through the clinic number, or to seek urgent/emergent care.

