### **Statistical Methods**

We will divide our cohort into 4 groups: Ambulatory Hypotension/Clinic Hypotension, Ambulatory Normotension/Clinic Normotension, Ambulatory Hypotension/Clinic Normotension, Ambulatory Normotension/Clinic Hypotension.

Our primary outcome will be acute kidney injury, defined as a doubling in serum creatinine from outpatient baseline requiring hospitalization. Baseline will be defined as the most recent outpatient serum creatinine prior to enrollment in this study. Death will be defined as death.

Survival analyses will determine the unadjusted and adjusted association of our 4 groups and AKI and death. We will censor those lost to follow-up. We will adjust for the variables obtained during our record review.

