## **Sample Size Justification**

Based on prior literature, we suspect the following distribution in our 4 groups: 50% ambulatory normotensive/clinic normotensive; 25% ambulatory hypotensive/clinic hypotensive; 12.5% ambulatory hypotensive/clinic normotensive; 12.5% ambulatory normotensive/clinic hypotensive. As best we can estimate 20% of the ambulatory normotensive/clinic normotensive group; 45% of the ambulatory hypotensive/clinic hypotensive group; 40% of the ambulatory hypotensive/clinic normotensive; and 40% of the ambulatory normotensive/clinic hypotensive group will develop AKI during 1-year of follow-up. Based on these effect sizes, we found that we would need to recruit 274 patients to have 80% power to detect at a significance level of 0.05.

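### Masked hypotension is defined by a bare count (more than one episode) over up to 730 home readings, so the Aim 1 proportion depends partly on how many readings each patient took; if the same count forms the four outcome groups, the death comparison is biased too

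*Combined protocol and SAP*

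**What the plan says.** The Aims section defines the burden of masked hypotension as the "Proportion of patients with normal clinic visit mean arterial blood pressure but with >1 episode of ambulatory hypotension". This is the only rule for ambulatory hypotension in the document. It gives no denominator, minimum number of readings, window or pressure cut, and does not say what counts as an episode.

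On the readings, Design says "participants will be asked to take their ambulatory blood pressure twice daily (i.e., morning and night", for 1 year. Procedures/Methods adds planned gaps: "Should patients be hospitalized or traveling, we will instruct patients to not perform any measurements". Text reminders are elective. If patients "do not complete their measurements for a 72-hour period, then a member of the research team will call them". Consent Procedures sets a completion level above 75%, but only as a condition for the gift card.

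On the outcomes, Statistical Methods names four ambulatory/clinic groups and says "Survival analyses will determine the unadjusted and adjusted association of our 4 groups and AKI and death". It does not say how or from when a patient belongs to a group. The primary outcome, AKI, is "a doubling in serum creatinine from outpatient baseline requiring hospitalization". After the measurement year, "we will review their records every 6 months for an additional 2-years (3-years total". The Sample Size Justification expects "25% ambulatory hypotensive/clinic hypotensive; 12.5% ambulatory hypotensive/clinic normotensive", so 37.5% ambulatory hypotensive in all and 12.5% masked.

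**The concern.** With a fixed count as the threshold, every extra reading is another chance to cross it. Two patients with the same blood pressure can get different labels because one measured more often. Reading counts will differ between patients: reminders and calls reduce gaps but do not equalise them, readings pause for travel and hospital stays, and they end at death. The Aim 1 proportion then mixes blood pressure with adherence and survival.

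If the same count, taken over the whole year, also forms the four groups, the number of readings is tied to the outcome. A patient who dies in month 2 has had about 120 chances to be labelled; a survivor has had up to 730. That pushes early deaths into the normotensive groups, against the study's own hypothesis. For AKI, readings may resume after discharge, so the label would draw on readings taken after the event it is meant to precede.

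**Working it through.** **Number of readings.** 2 × 365 = 730. At one minute each this is 730/60 = 12.2 hours, which agrees with the plan's estimate of about 12 hours. The 75% payment level is 0.75 × 730 = 547.5, about 548.

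**One patient.** Assume that one episode is one low reading and that readings are independent with low-reading rate q. Then P(labelled) = 1 − (1−q)^n − nq(1−q)^(n−1). For q = 0.5% and n = 365: 1 − 0.160 − 0.294 = 0.545. The probability is 23%, 55%, 76% and 88% at n = 182, 365, 548 and 730. At q = 5% it is already 94% by 90 readings, so the dependence matters most when low readings are infrequent.

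**Masked share (Aim 1).** The documents give no low-reading rate, so a model is needed. Patient mean pressure is μ ~ N(0, ρ), each reading adds N(0, 1−ρ), and ρ (the between-patient share of variance) is assumed to be 0.3 to 0.9. There is one clinic reading, with its cut c set so that 37.5% are low in clinic (25% + 12.5% in the Sample Size Justification). The home cut h is solved so that the masked share is the planned 12.5% at 730 readings. Masked share at n = average over μ of P(clinic reading ≥ c) × P(at least 2 of n home readings < h).

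| ρ | 730 | 548 | 365 | 182 |
|---|---|---|---|---|
| 0.3 | 12.5% | 10.2% | 7.4% | 3.8% |
| 0.5 | 12.5% | 10.7% | 8.4% | 5.2% |
| 0.7 | 12.5% | 11.1% | 9.2% | 6.4% |
| 0.9 | 12.5% | 11.5% | 10.2% | 7.9% |

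For scale, the sampling half-width for 12.5% of 274 is 1.96 × √(0.125 × 0.875/274) = 3.9 points. The loss at 548 readings (1.0-2.3 points) is below that; at 182 readings (4.6-8.7 points) it is above.

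**Contrast with a percentage rule.** Set the same model to 37.5% ambulatory hypotensive overall at 730 readings. An illustrative rule of at least 10% of readings low labels 36.8-37.5% at all four counts. The count rule falls to 17-32% at 182.

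**Death, only if the whole-year count forms the groups.** Same model at 37.5% labelled with 730 readings. Further assumptions are 10-30% yearly mortality, constant hazard, stable pressure and full adherence until death, and a label from all readings up to death or day 365. The rate ratio is deaths per person-time, hypotensive over normotensive.

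| True ratio | 1 year | 3 years |
|---|---|---|
| 1.0 | 0.52-0.83 | 0.76-0.94 |
| 2.0 | 0.82-1.54 | 1.22-1.78 |

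The true ratio of 2.0 applies to the 37.5% of patients with the lowest means. Values below 1 for a true 2.0 occur only over 1 year and only at ρ = 0.3; at ρ = 0.5 the 1-year ratio is 1.03. Giving everyone all 730 readings returns 1.70-1.93, so most of the attenuation comes from readings cut off by death. Labelling from the first 30 days with the 10% rule, and starting follow-up at day 30, returns 1.00 under no effect and 1.70-1.94 under a true 2.0.

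**AKI, same condition.** The planned 1-year risk is 0.5 × 20% + 0.25 × 45% + 0.25 × 40% = 31.25%, or 85.6 of 274. With an assumed 14-30 day pause and readings then resumed, the ratio under no effect is 0.94-1.00. However, 47-51% of an AKI patient's readings then come after the event.

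**The case against.** The strongest objection concerns the outcome aims. The count appears once, inside the definition of masked hypotension. Aims 2 and 3 speak of ambulatory blood pressure, and Statistical Methods gives no grouping rule. The planned shares even sit badly with the count if home and clinic use one cut: in the same model, more than one low reading in 730 labels 73-100% of patients and leaves about 0.01% or less in the ambulatory normotensive/clinic hypotensive group, where the plan expects 12.5%. This stands, and it is why the outcome results above are conditional.

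The size also depends on low readings being infrequent. With a shared cut, overall ambulatory hypotension moves only from 67.5% to 73.0% between 182 and 730 readings at ρ = 0.9, and from 99.8% to 100% at ρ = 0.3. That stands too, but the documents give neither a cut nor a rate that would establish this favourable case.

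A count can also be defended as the better measure of recurrent episodes. That is fair, and the fix allows for it; it does not excuse unequal observation time.

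Two stronger readings are tempting. A reader might infer that the plan would show real harm as protection. The model gives that for a true ratio of 2.0 only in one corner of the range and only over 1 year, while records are followed for 3 years; a fall in pressure before death, not modelled, would push the other way. A reader might also infer that the primary AKI comparison suffers the same count bias as death. That would need readings to stop for good at the AKI, which gives 0.52-0.83. The documents stop readings during the hospital stay and do not say that they end there.

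**Conclusion.** The concern holds for Aim 1 with high confidence. As written, the masked-hypotension proportion rises with the number of readings, and nothing in the plan sets a minimum or a common window. The effect is modest if most patients reach the payment level and large if completion is low. The figures assume that one episode is one low reading, that readings are independent within a patient, and that the planned 12.5% applies at full completion.

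For Aims 2 and 3 confidence is moderate, because the certain defect is only that no rule or date for forming the groups is given. If the whole-year count is used, the death association is biased towards hypotension looking protective. For AKI the count bias is small provided readings resume, and the main problem is exposure measured partly after the outcome. This should be settled before analysis.

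**What to change.** **Definition.** Define an episode and the mean arterial pressure cut, and set a minimum number of valid readings. Then either make the primary label a prespecified percentage or rate of low readings, or keep more than one episode within a fixed window of equal length for everyone and report it beside the rate of low readings per 100.

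**Aims 2 and 3.** State how the four groups are formed and use only readings taken before the event. Two ways are a fixed early window with follow-up starting at its end, or a time-updated exposure based on a rate and not on a cumulative count.

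The study team should choose and justify the cut, percentage, minimum and window. The 10% and 30 days used above are illustrations.

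**Cost.** Wording and analysis only; no new data.
- Patients with too few readings are unclassified.
- The group shares in the Sample Size Justification, and so the 274, must be restated for the chosen rule.
- A fixed early window drops events inside it. With the planned risks and constant hazard, 274 × Σ share × [1 − (1 − risk)^(d/365)] gives 8.6 of 85.6 first-year AKI events at d = 30 and 24.8 at d = 90. At an assumed 10-30% yearly mortality, a 30-day window also drops about 2-8 deaths.
- A time-updated exposure avoids most of that loss but needs a more complex model.

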### Design:

This is an observational study. We will approach patients with cirrhosis who are seen at the outpatient UCSF Liver Clinics. If willing, patients will be provided an ambulatory blood pressure monitor with an integrated cellular signal (i.e., not wifi or bluetooth) that is listed on the US Blood Pressure Validated Device database (VDL). After an instructional meeting at the time of enrollment, participants will be asked to take their ambulatory blood pressure twice daily (i.e., morning and night). Participants will partake in this study for 1-year. The ambulatory data will be provided to the researchers through an encrypted, HIPAA compliant server provided by the blood pressure monitor manufacturer (i.e. Withings). Simultaneously, we will periodically (i.e., monthly) review the participant's medical records and will extract clinic visit notes including clinic visit blood pressure measurements, demographics, hospitalization records, and all available laboratory values. After 1-year, the cellular signal on the device will be disabled. The participant will be able to keep the device for their own personal use. After 1-year, we will review their records every 6 months for an additional 2-years (3-years total). We will investigate the proportion of patients who experience masked hypotension. We will determine the association between ambulatory blood pressure and clinic visit blood pressure and the development of AKI and mortality.

### Background and Significance:

Cirrhosis affects 1 in every 50 US adults and is the 4th leading cause of death in those ages 45-64 years. Acute kidney injury (AKI) in patients with cirrhosis is: i) common, occurring in one of every two patients; ii) lethal with nearly 75% of patients having AKI at death; iii) expensive, hospitalizations in cirrhosis patients with AKI cost ~\$2 billion in 2016. A common risk factor of AKI in cirrhosis patients is hypotension. Patients with cirrhosis intrinsically have low blood pressure - a consequence of the altered venous return from portal hypertension and the impaired degradation by the liver of endogenous vasodilatory molecules. Despite this association, blood pressure in cirrhosis patients is currently only measured sparsely - every 3 to 6 months at

clinic visits. As a result, the burden of ambulatory hypotension and the impact of ambulatory hypotension on AKI and mortality in this population are unknown.

### **Preliminary Studies:**

To date, no study in cirrhosis patients has investigated ambulatory blood pressures in cirrhosis patients. One study by Tsien et al has investigated the association between clinic visit blood pressure and the development of AKI. No study has investigated the association between ambulatory or clinic visit blood pressure on mortality in cirrhosis patients.

### **Procedures/Methods:**

Patients will undergo the following procedures to this study:

1. We will pre-screen patients coming to the UCSF outpatient liver clinic 48 hours prior to their visit.
2. To set the device and allow for distribution at the time of their visit, we will call all possible participants 48 hours prior to their clinic visit and determine if they are interested in partaking in this study.
3. After their clinic visit, potential participants will be approached and provided the consent for this study. If willing, participants will be enrolled, provided a 5-minute device tutorial, and participants will be given the device on their visit day.
4. After which, participants will complete a morning blood pressure (e.g., prior to breakfast) and nighttime blood pressure (e.g., prior to sleep) for 1-year.
5. Patients at the time of enrollment will elect if they would like free text message reminders if they do not complete their measurements for a 24-hour period. If participants, do not complete their measurements for a 72-hour period, then a member of the research team will call them to remind all patients.
6. Should patients be hospitalized or traveling, we will instruct patients to not perform any measurements.
7. All measurements will be provided to the researchers through an encrypted, HIPAA compliant portal provided by the manufacturer (Withings).
8. We will review their medical records monthly for a 1-year period and every 6 months for an additional 2-year period. This review will include all clinic notes, demographics, and laboratory values.

There will be no extra clinic visits, lab tests, biopsies, tissue collection, or additional scans outside the routine care and monitoring provided by the UCSF Liver Clinic. We will not monitor the portal for episodes of hypotension in real-time - meaning that if a patient has hypotension, they will not be called to review for symptoms. Instead, at the time of consent and the monitor tutorial, we will review with patients the signs and symptoms of hypotension. We will instruct patients to review any new developments with their provider, who can be reached 24 hours 7-days a week through the clinic number, or to seek urgent/emergent care.

### **Statistical Methods**

We will divide our cohort into 4 groups: Ambulatory Hypotension/Clinic Hypotension, Ambulatory Normotension/Clinic Normotension, Ambulatory Hypotension/Clinic Normotension, Ambulatory Normotension/Clinic Hypotension.

Our primary outcome will be acute kidney injury, defined as a doubling in serum creatinine from outpatient baseline requiring hospitalization. Baseline will be defined as the most recent outpatient serum creatinine prior to enrollment in this study. Death will be defined as death.

Survival analyses will determine the unadjusted and adjusted association of our 4 groups and AKI and death. We will censor those lost to follow-up. We will adjust for the variables obtained during our record review.

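### Statistical Methods relates the four ambulatory/clinic groups to AKI and death without an exposure window or time origin, although every ambulatory reading is taken during follow-up

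*Combined protocol and SAP*

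**What the plan says.** In the combined protocol and SAP, Statistical Methods sets up the exposure with "We will divide our cohort into 4 groups: Ambulatory Hypotension/Clinic Hypotension, Ambulatory Normotension/Clinic Normotension" and the two discordant combinations. The analysis is "Survival analyses will determine the unadjusted and adjusted association of our 4 groups and AKI and death". That section ties only baseline creatinine to enrolment. It does not say which readings assign a patient to a group, over what period, against what cut-off, or when the clock starts.

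Procedures/Methods fixes when readings occur. Under item 3, "participants will be given the device on their visit day". Under item 4, "participants will complete a morning blood pressure (e.g., prior to breakfast) and nighttime blood pressure (e.g., prior to sleep) for 1-year". Item 6 adds "Should patients be hospitalized or traveling, we will instruct patients to not perform any measurements", and item 5 provides for resumption: "If participants, do not complete their measurements for a 72-hour period, then a member of the research team will call them".

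The nearest thing to an exposure rule is in Aims, for the burden of masked hypotension only: "Proportion of patients with normal clinic visit mean arterial blood pressure but with >1 episode of ambulatory hypotension". It has no window, and an episode is not defined. Sample Size Justification plans AKI risks over 1 year. Design collects clinic pressures throughout follow-up and continues record review to 3 years, with ambulatory transmission ending after the first.

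**The concern.** Exposure is measured while patients are already at risk. If a full year of readings is used to label patients and survival time is counted from enrolment, two things can go wrong.

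- **Time at risk.** A count of low readings can only grow with observation. A patient who dies early, or whose readings stop for good at AKI, has fewer chances to reach the count and tends to be labelled normotensive. This pushes the hazard ratio down.
- **Order of events.** AKI may be followed by lower pressure at home. If those later readings count, the consequence is entered as the predictor. This pushes the hazard ratio up.

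Both association aims rest on these groups. Adjusting for record-review covariates removes neither problem, because the error lies in how exposure is assigned in time. The clinic half is open to the same difficulty, since clinic pressures also accrue during follow-up. Leaving the rule open also allows the window to be chosen after the data have been seen.

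**Working it through.** The plan gives no figure for this bias, so none can be reproduced. Its group shares and AKI risks (Sample Size Justification) set the scale. Everything marked *assumed* is absent from the documents.

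**1. AKI rate.** Cohort risk = 0.50×0.20 + 0.25×0.45 + 0.125×0.40 + 0.125×0.40 = 0.3125. Expected events = 274×0.3125 = 85.6, about 86. Constant hazard = −ln(1−0.3125) = 0.375 a year. The planned 40% v 20% contrast corresponds to HR = ln(0.6)/ln(0.8) = 2.29.

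**2. Spread between patients.** Each margin is 25 + 12.5 = 37.5% hypotensive, with 25% hypotensive on both. A bivariate normal with those margins needs correlation 0.676. Treat the clinic value as one reading and the ambulatory value as the long-run mean (*assumed*). Then within-patient SD = between-patient SD × √(1/0.676² − 1) = 1.09 × between-patient SD, for example 8 → 8.7 mmHg. Choose the cut-off so that 37.5% of patients have more than one low reading in 730. The log of the per-reading probability then has an SD of about 3.2, whether the between-patient SD is 6, 8 or 10 mmHg.

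**3. Why a count depends on survival.** As an illustration, a patient averaging 2 low readings in a full year exceeds one with probability 1 − 3e⁻² = 0.59. Observed for half the year, the probability is 1 − 2e⁻¹ = 0.26. The patient is the same but the label differs.

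**4. Simulated HR when the true HR is 1.** AKI or death is independent of pressure. There were 200,000 to 400,000 patients per scenario, for the ambulatory contrast only. One low reading is taken as an episode (*assumed*), at the spread in step 2.

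| Count rule, whole year, time from enrolment | HR |
|---|---|
| AKI; 7-28 day pause, readings then unchanged | 0.96-1.01 |
| AKI; low readings ×1.5 afterwards (*assumed*) | 1.07-1.10 |
| AKI; ×2 afterwards (*assumed*) | 1.16-1.20 |
| AKI; ×3 afterwards (*assumed*) | 1.29-1.34 |
| AKI; readings end for good (*assumed*) | 0.60-0.65 |
| Death at 10-20% a year (*assumed*), 1 year | 0.60-0.65 |
| Same death rates, 3 years | 0.82-0.86 |

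The first row is closest to Procedures/Methods items 5 and 6, though the pause length is itself assumed.

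**5. Average rule.** With groups defined by whole-year mean arterial pressure (MAP), early stopping gives about 1.00. If MAP is 2, 5 or 10 mmHg lower after AKI (*assumed*), the HR is about 1.15-1.27, 1.4-1.8 or 2.1-3.2 for between-patient SDs of 10 down to 6 mmHg (*assumed*).

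**6. The definition is itself unsettled.** The planned shares include "12.5% ambulatory normotensive/clinic hypotensive", which is 12.5/62.5 = 20% of ambulatory normotensives. If an episode is one low reading, an ambulatory normotensive has at most 1 low in 730 (0.14%). The two are hard to square unless the clinic cut-off differs. The shares fit an average-based rule more easily.

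**The case against.** The strongest reply is that the plan never says groups are fixed from a year of readings. An early window or time-updated groups would both fit the text. That stands: the bias is conditional, and what is certain is the omission. A reader might infer that the plan commits to an immortal-time error, but the documents do not support that.

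Second, items 5 and 6 of Procedures/Methods only pause readings in hospital and then prompt patients to resume. That also stands. On that path the AKI bias is nearly null. Larger AKI distortion needs readings to end for good or pressure to stay lower afterwards, and no passage states either. For death, readings do end. But the 1-year figure is tied to no stated horizon for death; over the 3 years in Design the effect is smaller.

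Third, the inputs are assumed. A reader might also infer far larger count-rule distortions, with hazard ratios near 0.3 or above 3. Those arise only when patients differ little in their tendency to low readings. The planned shares imply a log-SD of about 3.2, so they do not support those cases.

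Finally, a 30-day landmark leaves most of the readings out of the primary analysis. That is fair: 30 days is one acceptable choice, and the lagged sensitivity analysis uses the rest.

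**Conclusion.** The point holds as a cheap improvement. Statistical Methods needs an exposure window and a time origin, and no other section supplies them. If whole-year readings were combined with time from enrolment, the bias could run either way. It would be negligible for AKI under a simple pause. It would be downward for death under a count rule, and upward for AKI if pressure stays lower afterwards. At the larger assumed falls under an average rule, the spurious HR reaches the size of the planned contrast of 2.29. These sizes rest on assumed death rates, pause lengths, pressure changes and between-patient SDs, and the count-rule figures also on equating an episode with one low reading. The documents settle neither size nor direction, so the simulations show what the omission permits and do not predict the result.

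**What to change.** In Statistical Methods, state that only readings preceding the time at risk define exposure.

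- **Primary analysis.** Classify clinic pressure from the enrolment visit. Classify ambulatory pressure from a pre-stated early window (30 days is one example), using a measure that does not grow with the number of readings, such as mean MAP or the proportion of low readings, with the cut-off fixed in advance. Start the clock for AKI and death at the end of the window and report earlier events descriptively.
- **Sensitivity analysis.** Use time-updated exposure from readings before each event, with a pre-stated lag so that the illness leading to admission is not counted as exposure. Exclude readings after AKI from the AKI analysis. State how exposure is carried into years 2-3 for death.

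**Cost.** No new data are needed. AKI events before the landmark are 274×(1−exp(−0.375×30/365)) = 8.3 by day 30, leaving about 77 of 86; by day 90 the figure is 24.2. Under the model in step 2, a 30-day mean puts about 96% of patients in the same group as their long-run mean. The group shares and power in Sample Size Justification should be restated for the chosen definition.

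### Home and clinic pressure enter the association analyses only as four yes/no groups; a prespecified continuous model beside them would answer Aims 2 and 3 better

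*Combined protocol and SAP*

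**What the plan says.** Aim 2 asks: "What is the association between ambulatory blood pressure and clinic visit blood pressure and the development of acute kidney injury". Aim 3 asks the same about death. Neither names a scale for pressure.

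Statistical Methods crosses ambulatory hypotension (yes/no) with clinic hypotension (yes/no): "We will divide our cohort into 4 groups". The only association analysis follows from that: "Survival analyses will determine the unadjusted and adjusted association of our 4 groups and AKI and death". No model with pressure as a continuous variable appears anywhere.

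No cut-off in mmHg is stated. Aim 1 defines masked hypotension through an episode count: "normal clinic visit mean arterial blood pressure but with >1 episode of ambulatory hypotension".

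Sample Size Justification expects these group shares: "50% ambulatory normotensive/clinic normotensive", "25% ambulatory hypotensive/clinic hypotensive", "12.5% ambulatory hypotensive/clinic normotensive" and "12.5% ambulatory normotensive/clinic hypotensive". The expected one-year AKI rates are 20%, 45%, 40% and 40% in that order. It attaches 80% power at the 0.05 level to 274 patients.

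**The concern.** Two readings a day for a year give up to 2 × 365 = 730 home readings per patient, and the planned model uses one yes/no label made from them. Patients just either side of the cut count as different, and patients far apart on the same side count as alike. If risk changes smoothly with pressure, this costs power.

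The second consequence matters more for what the study adds. Its new question is whether home pressure tells us something that clinic pressure does not. Home and clinic pressure are correlated, and yes/no clinic status adjusts only partly for clinic pressure. Home status can pick up what is left over, so a masked-hypotension effect could appear where none exists.

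**Working it through.** **1. The plan's own figure.** Take a 3-df chi-square test across the four groups, for which 80% power at 0.05 needs a noncentrality of 10.90. The effect per patient is the weighted variance of the rates divided by p̄(1 − p̄).
- Four equal groups: p̄ = 0.3625 and variance 0.009219, so 0.009219/0.2311 = 0.03989. N = 10.90/0.03989 = 273.3, which rounds up to 274. This reproduces the stated figure.
- The stated 50/25/12.5/12.5 split: p̄ = 0.3125 and variance 0.01297, so 0.01297/0.2148 = 0.06036. N = 181. At 274 the noncentrality is 16.54 and power is 94.2%.

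So 274 fits equal groups, not the stated shares. That is a separate matter, but it means two starting points are needed below.

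**2. Assumptions for the comparison (not in the documents).** Home and clinic mean arterial pressure (MAP) are bivariate normal, each is cut at one value, and the effect is linear. Each margin is 25 + 12.5 = 37.5%. The latent correlation that gives a 25% joint share with those margins is 0.676. One-year AKI is treated as binary, as an approximation to the survival analysis.

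**3. Information kept.**
- One pressure cut once: φ(z)²/[p(1 − p)] at p = 0.375 is 0.3792²/0.2344 = 0.613.
- Four groups against two continuous terms, as the share of the variance of the linear index that the groups explain: 0.701 if both pressures matter equally, 0.648 if only one matters. The loss is 30–35%.

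**4. Power, four groups (3 df) against two continuous terms (2 df).**

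| Starting point | Four groups | Continuous | Gap |
|---|---|---|---|
| Four-group test at the stated 80% | 80% | 95.1–96.5% | 15–17 points |
| Plan's split and rates, N = 274, linear effect | 94.2% | about 99.5% | about 5 points |
| Plan's group rates exactly true (near-step) | 94.2% | 84.9% (linear) | −9 points |

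In the first row the continuous noncentrality is 10.90/0.701 = 15.5, or 10.90/0.648 = 16.8. In the second it is 16.54/0.701 = 23.6. In the third it is 274 × 0.0398 = 10.9 on 2 df.

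**5. Does home status add to clinic status?** Logistic simulations used the same bivariate normal pressures, with only clinic pressure affecting AKI. Testing home status given yes/no clinic status at nominal 5% rejected falsely in 9% of studies at a log-odds of 0.5 per SD and in 14% at 0.8. A second set of simulations gave about 12–17%. With both pressures continuous, the rate stayed at about 5%.

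**The case against.** The case for the four groups is substantial.

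- **They match the hypothesis.** The Hypothesis section concerns whether hypotension occurs outside the clinic and whether that occurrence goes with morbidity and mortality. Occurrence is categorical. This stands, and it is why the groups should not be replaced.
- **The expected rates are near a step.** At 20/40/40/45%, most of the rise comes with any hypotension at all. If that is exact, a linear model has less power (85% against 94%), and three-knot splines on both pressures have less still (about 77–79%). The arithmetic stands. But the plan offers these rates only as a best estimate, and Preliminary Studies says ambulatory pressure has not been studied in cirrhosis, so a step at an unnamed threshold is not established.
- **An episode count is not a cut mean.** Mean MAP can miss intermittent hypotension. This stands: the continuous term is a different exposure, and the loss figures apply only to a cut on a mean.
- **The groups already compare home status within clinic status, and allow an interaction.** True, but the comparison is within clinic status, not at equal clinic pressure. That leftover difference produces the false positives in step 5.
- **A continuous model brings its own costs.** Under a linear effect, splines take 80% power to about 70%. A full-year mean of home pressure, entered as a fixed term, would use readings taken after follow-up for AKI has begun. Both points stand and shape the fix.

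**Conclusion.** The point holds as a moderate improvement. The plan has no continuous-pressure model although Aims 2 and 3 ask about the pressures. If risk is smooth and linear, the four groups lose about 30–35% of the information. The power cost is 15–17 points if the four-group test has its stated 80%, and about 5 points at the plan's own split and rates. The sign reverses if the near-step rates are exactly right. The incomplete adjustment for clinic pressure (about 9–17% false positives against about 5%) is the stronger reason to act. It too rests on simulated normal pressures and on how strongly clinic pressure affects risk.

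A reader might infer three stronger things that the documents do not support:
- **A 39% loss.** The 38.7% (1 − 0.613) is for one pressure cut once, not for the four-group analysis.
- **A loss of about 20 points of power.** Losses that large arise when the continuous model is the one set at 80–90%. Sample Size Justification attaches its 80% to the four groups.
- **That the grouping wastes power whatever the truth, and should be dropped.** The loss depends on the shape of the effect, and the hypothesis itself concerns the occurrence of hypotension.

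**What to change.** Keep the four-group survival analysis for the hypothesis and the masked-hypotension question. Add to Statistical Methods:

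1. A prespecified Cox model for AKI, and one for death, with home MAP and clinic MAP as continuous terms. Report the home-MAP effect adjusted for clinic MAP.
2. A restricted cubic spline check for non-linearity.
3. A rule that home MAP uses only readings taken before the risk period: either a fixed early window with follow-up counted from a landmark at its end, or a time-updated mean. The full-year mean should not be entered as a fixed covariate.

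The cost is SAP wording and one extra model per outcome, on data already being collected. The downsides are an assumed functional form, some loss of power where splines are used, and a mean that may miss intermittent hypotension, which the retained groups cover. A landmark also leaves events inside the early window out of that model.
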